1.2.8 Structure of NCI-4650

A schematic of NCI-4650 is provided in (**Figure 5**). NCI-4650 is chemically identical to naturally occurring mammalian mRNA with the exception that the uridine nucleoside normally

present in mammalian mRNA is fully replaced with N1-methyl-pseudouridine, a naturally occurring pyrimidine base present in mammalian tRNAs^{20, 21}. The cap structure used in NCI-4650 is identical to the natural mammalian Cap 1 structure^{22, 23}. Each mRNA construct will be between 500 and 3000 nucleotides in length coding for neoantigens between 15 and 41 amino acids in length.

Abbreviations: UTR = untranslated region; ORF = open reading frame.

Figure 5. Schematic of mRNA-4650 design.

1.2.9 Risk for NCI-4650 Monotherapy

The risk to subjects receiving NCI-4650 is expected to be low and primarily involving mild to moderate toxicities which have been observed in animal studies and generally observed and expected for other IM administered vaccines. These local reactions may consist of transient and dose-dependent pain, swelling, and erythema. Possible mild to moderate systemic reactions, which are also transient, may include fever, fatigue, chills, headache, myalgias, and arthralgias. Such AEs may, in part, be due to the poor biodegradability of LNP formulations used in other vaccine studies; the LNP that comprises NCI-4650 is designed to have superior biodegradability and thus may have a further improved safety profile. Also, other AEs that have generally been associated with approved IM administered vaccines have included mild hematological and clinical chemistry abnormalities, which are usually reversible. Subjects receiving NCI-4650 could experience signs and symptoms compatible with a C activation-related pseudoallergy (CARPA) response, which has been observed in the administration of approved liposomal products, contrast agents, pegylated proteins, and antibodies²⁴, as well as for small interfering RNA products formulated in LNPs^{25, 26}. The signs and symptoms of CARPA resemble those of an acute hypersensitivity reaction. However, complement activation is far less likely to be associated with clinical signs for LNP products such as NCI-4650, which are administered IM at a much lower dose on a mg/kg basis than other clinical entities that cause CARPA in humans and nonclinical species.

The design of this study allows an escalation of dose with intensive safety monitoring to ensure the safety of subjects, the study will use a traditional "3+3" design. Any potential safety risks, such as ISRs, will be monitored closely throughout the study. Dosing will be staggered by three weeks between the first dose administered to the first patient and the first dose administered to the second patient in Dose Level 2 (starting dose level) of the Phase I Cohort for safety monitoring purposes. Subsequent patients may begin treatment at an interval of one week.

2 ELIGIBILITY ASSESSMENT AND ENROLLMENT

2.1 ELIGIBILITY CRITERIA

2.1.1 Inclusion Criteria

- 2.1.1.1 Measurable (per RECIST v1.1 criteria), metastatic melanoma, gastrointestinal, or genitourinary cancer with at least one lesion that is resectable. Only patients with metastatic gastrointestinal cancer will be eligible for enrollment on the Phase I portion of the study. Patients with metastatic melanoma, gastrointestinal, or genitourinary cancer will be eligible for enrollment on the Phase II portion of the study.
- 2.1.1.2 Confirmation of diagnosis of metastatic cancer by the NCI Laboratory of Pathology.
- 2.1.1.3 Patients with 3 or fewer brain metastases that are < 1 cm in diameter and asymptomatic are eligible. Lesions that have been treated with stereotactic radiosurgery must be clinically stable for one month after treatment for the patient to be eligible. Patients with surgically resected brain metastases are eligible.
- 2.1.1.4 Prior therapy with at least one first-line standard of care treatment or second-line treatment of proven effectiveness. Patients must have progressive disease after prior treatment. Prior first- or second-line treatments would include the following:
 - Patients with metastatic melanoma: Receipt of a checkpoint inhibitor as first-line therapy.
 - Patients with metastatic melanoma with an activating mutation of *KIT*: Receipt of imatinib.
 - Patients with a BRAF V600 activating mutation: Receipt of appropriate targeted therapy.
 - Patients with metastatic gastrointestinal cancer: Receipt of up to two forms of approved first- and/or second-line chemotherapy regimens.
 - Patients with metastatic genitourinary cancers: Receipt of a first- or second-line therapy appropriate for their histologic subtype.
- 2.1.1.5 Age \geq 18 years and \leq 70 years.
- 2.1.1.6 Clinical performance status of ECOG 0 or 1 (see Appendix B).
- 2.1.1.7 Women of child-bearing potential must have a negative pregnancy test because of the potentially dangerous effects of the treatment on the fetus.
- 2.1.1.8 Serology
 - Seronegative for HIV antibody. (The experimental treatment being evaluated in this protocol depends on an intact immune system. Patients who are HIV seropositive may have decreased immune-competence and thus may be less responsive to the experimental treatment and more susceptible to its toxicities.)
 - Seronegative for hepatitis B antigen, and seronegative for hepatitis C antibody. If hepatitis C antibody test is positive, then the patient must be tested for the presence of antigen by RT-PCR and be HCV RNA negative.

- 2.1.1.9 Hematology
 - ANC > 1000/mm³ without the support of growth factors.
 - WBC \geq 3000/mm³
 - Platelet count \geq 100,000/mm³
 - Hemoglobin > 8.0 g/dL. Subjects may be transfused to reach this cut-off.

2.1.1.10 Chemistry

- Serum ALT/AST $\leq 5.0 \text{ x ULN}$
- Serum creatinine < 1.5 x ULN or measured creatinine clearance (calculated using Cockcroft-Gault formula) > 40 mL/min
- Total bilirubin \leq 2.0 mg/dL, except in patients with Gilbert's Syndrome, who must have a total bilirubin < 3.0 mg/dL.
- 2.1.1.11 More than four weeks must have elapsed since any prior systemic therapy at the time the patient receives the immunization regimen, and patients' toxicities must have recovered to a grade 1 or less (except for toxicities such as alopecia or vitiligo).
- 2.1.1.12 Ability of subject to understand and the willingness to sign a written informed consent document.
- 2.1.1.13 Subjects must be co-enrolled on protocol 03-C-0277.
- 2.1.2 Exclusion Criteria
- 2.1.2.1 Pregnant or breastfeeding women who do not consent to stop breastfeeding while on study treatment and for 30 days after the use of the investigational vaccine, where pregnancy is confirmed by a positive, rising hCG laboratory test.
- 2.1.2.2 Women of child-bearing potential, defined as all women capable of becoming pregnant, unless they agree to use an appropriate method of contraception during dosing and for 120 days after the last dose (i.e., final vaccine). Effective contraception methods include a combination of any two of the following (unless method is abstinence or sterilization, in which only one method is required):
 - Use of oral, injected, or implanted hormonal methods of contraception, or other forms of hormonal contraception that have comparable efficacy (failure rate < 1%). In case of use of oral contraception, women should have been stable on the same pill for a minimum of 6 months before taking study treatment.
 - Placement of an intrauterine device or intrauterine system.
 - Barrier methods of contraception: condom or occlusive cap (diaphragm or cervical/vault caps) with spermicidal foam/gel/film/cream/vaginal suppository.
 - Total abstinence
 - Female sterilization at least eight weeks before taking study treatment.
 - Male sterilization (at least six months prior to screening).

- 2.1.2.3 Sexually active males must use a condom during intercourse during dosing and for 120 days after the last dose (i.e., final vaccine), and should not father a child in this period.
- 2.1.2.4 Any systemic steroid therapy or other form of immunosuppressive therapy within 7 days of the first dose of the vaccine. A physiologic dose of systemic corticosteroids may be approved. Inhaled or topical steroids, and adrenal replacement steroid doses ≤ 10 mg daily prednisone equivalent are permitted in the absence of active autoimmune disease.
- 2.1.2.5 Active systemic infections requiring anti-infective treatment, coagulation disorders, or any other active or uncompensated major medical illnesses of the cardiovascular, respiratory, or immune system.
- 2.1.2.6 Any form of primary immunodeficiency (such as Severe Combined Immunodeficiency Disease).
- 2.1.2.7 Concurrent opportunistic infections (The experimental treatment being evaluated in this protocol depends on an intact immune system. Patients who have decreased immune-competence may be less responsive to the experimental treatment and more susceptible to its toxicities).
- 2.1.2.8 Any vaccinations four weeks prior to the first vaccination cycle or live vaccines at any time during the study.

2.2 SCREENING EVALUATIONS

Note: Testing for screening evaluation is conducted under the NCI-SB companion protocol, 99-C-0128 (Evaluation for NCI Surgery Branch Clinical Research Protocols).

- 2.2.1 Within 3 Months Prior to Part Two Registration
 - HIV antibody titer, HBsAg determination, and anti-HCV
 - Confirmation of diagnosis of metastatic melanoma, gastrointestinal, or genitourinary cancer by the NCI Laboratory of Pathology. (Note: Testing is permitted to be conducted at any time prior to Part Two registration.)
- 2.2.2 Within 4 Weeks Prior to Part Two Registration
 - Complete history and physical examination. (Note: Patient history may be obtained within 8 weeks prior to Part Two registration.)
 - Imaging evaluation to determine baseline disease status. This may include CT, MRI, PET, and/or photography.
- 2.2.3 Within 7 Days Prior to Part Two Registration
 - Screening blood tests:
 - CBC w/differential
 - Chemistries: Creatinine, ALT/GPT, AST/GOT, Total bilirubin
 - Lymphocyte phenotyping (TBNK)
 - Urinalysis, with culture if indicated

- Physical examination, including ECOG of 0 or 1 (see Appendix B)
- Weight and vital signs
- β-HCG pregnancy test (serum or urine) on all women of child-bearing potential

2.3 REGISTRATION AND TREATMENT ASSIGNMENT PROCEDURES

2.3.1 Prior to Registration for this Protocol

Patients will initially sign the consent for and enroll on protocol 03-C-0277 prior to tumor harvest and leukapheresis for generation of the cell product. Patients will then sign the consent for and register for Part One of this treatment protocol. If the mRNA vaccine meets the requirements specified in the Certificate of Analysis (CoA) (**Appendix C**) to include USP <71> sterility testing, the vaccine will be released by Moderna and shipped to the NIH Clinical Center Pharmacy, where it will be dispensed and administered to the patient after receipt by the pharmacy of a physician's order. The patient must meet the eligibility criteria and be registered to Part Two of this treatment protocol before receiving the vaccine. If the mRNA vaccine does not meet the requirements specified in the CoA, the vaccine will not be released by Moderna and the patient will be taken off-study (Section **3.8.2**).

2.3.2 Registration Procedure

Registration will be a two-part process. Authorized staff must register an eligible candidate with the NCI Central Registration Office (NCI-CRO) within 24 hours of signing consent. To initially register a subject after the participant has signed the consent, complete the top portion of the registration Eligibility Checklist from the website

(http://home.ccr.cancer.gov/intra/eligibility/welcome.htm) indicating that the patient is being registered for Part One and send via encrypted email to the NCI-CRO at [contact].

Once the mRNA vaccine meets the requirements specified in the CoA and the vaccine is released by Moderna, and eligibility is confirmed after completion of screening studies, authorized staff must complete the remainder of the eligibility checklist, indicating that the patient is being registered for Part Two (treatment on study). Email the completed registration Eligibility Checklist to the NCI-CRO at [contact].

After confirmation of eligibility at the NCI-CRO, CRO staff will call pharmacy to advise them of the acceptance of the patient on the protocol prior to the release of any investigational agents. Verification of registration will be forwarded electronically via email to the research team. A recorder is available during non-working hours.

Subjects that do not meet screening criteria should be removed from the study following the procedure in Section **3.8.3**.

Note: Patients are not considered to be fully enrolled on this treatment protocol unless they meet the eligibility criteria and are registered to Part Two.

2.3.3 Treatment Assignment Procedures

2.3.3.1 Cohorts

Number	Name	Description
1	Phase I Gastrointestinal Cancer	First 12-18 patients enrolled with a diagnosis of gastrointestinal cancer
2a	Phase II Melanoma	Patients with a diagnosis of melanoma
2b	Phase II Gastrointestinal or Genitourinary Cancer	Patients with a diagnosis of gastrointestinal or genitourinary cancer

2.3.3.2 Arms

Number Name Description		Description	
	1	Phase I	Escalating doses of mRNA vaccine
	2	Phase II	MTD of mRNA vaccine established in Phase I

2.3.3.3 Randomization and Arm Assignment

[figure not shown]
This is a non-randomized study. All patients will be directly assigned based on cohort as follows:

- Subjects in Cohort 1 will be directly assigned to Arm 1.
- Subjects in Cohort 2a will be directly assigned to Arm 2.
- Subjects in Cohort 2b will be directly assigned to Arm 2.

3 STUDY IMPLEMENTATION

3.1 STUDY DESIGN

3.1.1 Schema

3.1.2 Pre-Treatment Phase: Performed on 03-C-0277

Patients with metastatic melanoma, gastrointestinal, or genitourinary cancers will undergo resection of the tumor and apheresis under protocol 03-C-0277. Whole exome sequencing will be performed under protocol 03-C-0277 to identify all cancer mutations using our standard procedures. TIL will be grown and expanded for this trial according to Standard Operating

Procedures (SOPs) which can be found in BB-IND 17858. After a sufficient yield of TIL ($5x10^7$ cells) is expanded, immunogenic neoantigens will be identified by high throughput immunologic screening using long peptides and tandem minigenes covering all mutated epitopes to identify the exact mutations recognized by autologous T-cells. Up to 15 predicted neoantigens will be selected based on exome and RNA sequencing and their binding affinity to the patient HLA molecules (see **Appendix A**). The final nucleotide sequences of the mutated 15-41mer epitopes and/or driver genes will then be transmitted electronically via Globus, a secure research data management system, to Moderna for production of the NCI-4650 drug product.

3.1.3 Treatment Phase

Patients will receive a mRNA-based vaccine IM at two-week intervals for four cycles. All patients may receive one course of treatment (four vaccination cycles). Immunologic tests will be performed as per Section **5.4** to quantitate circulating T-cells reactive with the immunizing antigens. If a 3-fold increase in the precursor level of pre-existing neoantigen-specific T-cells or new reactivity appears in the blood at detectable levels, patients may be vaccinated with a second and final course of treatment using the same vaccine dose. The second course may start approximately four weeks (± 2 weeks) from the last vaccine dose of the first course.

If the patient receives only one course of treatment (four vaccination cycles), the start date of the course will be the date of the first vaccination; the end date will be the date of the first post-treatment evaluation. If the patient receives a second course (four additional vaccination cycles), the start date of the first course will be the date of the first vaccination. The date of the fifth vaccination will be both the end date of the first course and the start date of the second course. The end date of the second course will be the date of the first post-treatment evaluation.

3.1.4 Dose-Limiting Toxicity

The dose-limiting toxicity (DLT) evaluation period for determination of the maximum tolerated vaccine dose (MTD) will occur during the 21 days after the first vaccination for each patient. A DLT is defined as follows: All grade 3 or greater toxicities related to the mRNA vaccine, with the exception of:

- Grade 3 fever
- Grade 3 pruritus/itching
- Grade 3 fatigue
- Grade 3 metabolic laboratory abnormalities without significant clinical sequela that resolve to grade 2 or less within 7 days.
- Grade 3 autoimmune toxicity that resolves to grade 2 or less within 7 days.
- Events that are clearly related to the patient's disease.
- 3.1.5 Phase I Dose Escalation

Subjects will receive their assigned dose level of NCI-4650 as IM injections on Days 0, 14, 28, and 42. The maximum dose of mRNA vaccine for each dose level will be:

Dose Level	vel NCI-4650, mRNA Vaccine Dose	
Level 1	0.04 mg (0.0006 mg/kg based on a 70-kg subject)	
Level 2	0.13 mg (0.0019 mg/kg based on a 70-kg subject)	
Level 3	0.39 mg (0.0056 mg/kg based on a 70-kg subject)	

Moderna is the sponsor of a dose escalation trial utilizing a nearly identical vaccine (mRNA-4157) as the mRNA vaccine used in this protocol (NCI-4650). The dose escalation in both protocols is the same (0.04 mg, 0.13 mg, and 0.39 mg). As indicated in the Moderna Safety Review Committee Dose Level Approval Form dated 21 December 2017, the Moderna Medical Monitor noted that for the three patients enrolled on Dose Level 1 (Part A) in the Moderna trial (0.04 mg mRNA-4157 monotherapy), no DLTs were experienced and the only AEs experienced were grade 1 injection site soreness, which is expected for the vaccine. As a result, Dose Level 1 was declared safe and tolerated. For this trial, because Dose Level 1 was shown to be safe and tolerated, the first two patients were enrolled on Dose Level 2. No DLTs were experienced and the only AEs experienced were grade 1 and 2 related events.

As indicated in the Moderna Safety Review Committee Dose Level Approval Form dated 13 July 2018, the Moderna Medical Monitor noted that for the six evaluable patients enrolled on Dose Level 2 (Part A) in the Moderna trial (0.13 mg mRNA-4157 monotherapy), no DLTs were experienced and the only AEs experienced were mild, non-serious grade 1 events considered to be related to the experimental treatment. Additionally, as indicated in the Moderna Safety Review Committee Dose Level Approval Form dated 07 September 2018, four evaluable patients were enrolled on Dose Level 2 (Part B) in the Moderna trial (0.13 mg mRNA-4157 in combination with pembrolizumab). These four patients experienced only mild, non-serious grade 1 events considered to be related to the experimental treatment, and no DLTs were seen. The following table shows all grade 1 events experienced by all patients enrolled on Dose Level 2 in the Moderna trial, for both parts A and B:

Adverse Events	Incidence	# of Patients
Injection site (edema, erythema, tenderness)	8	3
Diarrhea	2	1
Photosensitivity	1	1
Arthritis	4	3
Finger edema	1	1
Myalgias	4	3
Flu-like symptoms	1	1

For this trial, because Dose Level 2 has been shown to be safe and tolerated, we propose to enroll our third patient (previously anticipated to be the third patient in Dose Level 2) as the first patient in Dose Level 3. The protocol will enroll three patients at Dose Level 3 unless a patient experiences a DLT.

In each dose level, if a patient experiences a DLT, a total of six patients will be treated at that dose to confirm that no greater than 1/6 patients have a DLT prior to proceeding to the next higher dose level. If a level with 2 or more DLTs in 3-6 patients has been identified, patients will be accrued at the next-lowest dose level, for a total of 6 patients. If two DLTs occur in the second dose level (0.13 mg), the dose will be de-escalated to Dose Level 1 (0.04 mg). If two DLTs occur at Dose Level 1, the study will be temporarily halted, as described in Section **3.2**.

The MTD is the highest dose at which ≤ 1 of 6 patients experienced a DLT or the highest dose level studied if DLTs are not observed at any of the dose levels.

Although the MTD may be reached during this clinical study, determining the MTD is not the aim of the study as benefit from this therapeutic vaccine approach may be achieved at lower doses.

3.1.6 Rationale for Dose Level Regimen and Route of Administration

As described in the repeat-dose GLP toxicology studies in outbred Sprague Dawley rats described in Section **1.2.4** and IND 17390, the no-observed-adverse-effect-level (NOAEL) for mRNA-4157 was determined to be 0.035 mg based on the clinical and microscopic findings observed in this study. Based on HED, this represents an approximate 24-fold safety margin over the proposed human starting dose of 0.04 mg. The highest dose in the rat toxicology study was 0.117 mg (0.32 mg/kg), which is an approximate HED of 3.51 mg (0.05 mg/kg based on a 70-kg subject) and is approximately 88-fold higher than the proposed starting clinical dose of 0.04 mg. Thus, it is considered that a starting dose of 0.04 mg has an adequate safety margin.

The highest dose in the GLP rat toxicology study (0.117 mg; which is a HED of 3.51 mg based on a 70-kg subject) is approximately 9-fold higher than the highest planned clinical dose of 0.39 mg. The NCI-SB considers that this represents a sufficient safety margin to the dose levels in this clinical study. The 3+3-guided dose escalation scheme of approximately half-log (3-fold) increments (i.e., 0.04, 0.13, and 0.39 mg) is consistent with FDA guidance for early-phase clinical trials involving cellular and gene therapy products²⁷.

Subjects will receive their assigned dose level on Day 1 of each 14-day cycle (days 0, 14, 28, and 42). Four cycles of NCI-4650 are planned to boost the intended tumor-killing T-cell population over an extended period by promoting optimal development of T-effector memory cells. The 14-day cycle allows for maximal contraction of the antigen-specific CD8⁺ T-cells response before boosting, which found to produce best maintenance of CD8⁺ T-cells with high recall capacity. From a safety perspective, the Manufacturer assessed the toxicity of mRNA-4157 in Sprague Dawley rats at the dose levels of 0.012, 0.035, and 0.117 mg via IM injection every week for 4 weeks (5 doses in total; refer to Section **1.2.4** and IND 17390). This preclinical weekly injection schedule is 2-fold more dose-dense over time than the clinical dosing schedule in this study, and thus provides an additional margin to potential cumulative toxicity.

The IM route of administration was chosen for ease of administration.

3.1.7 Phase II Portion

Patients in Phase II will receive the MTD as determined in Phase I. The Phase II portion of the protocol will consist of two cohorts as defined in Section **2.3.3.1**: Cohort 2a, patients with melanoma and Cohort 2b, patients with gastrointestinal or genitourinary cancer.

The Phase II portion of the study will utilize an optimal design where initially 12 evaluable patients will be enrolled in each cohort. For each cohort, if 0 of the first 12 evaluable patients experience a clinical response, then no further patients will be enrolled; if 1 or more of the first 12 evaluable patients enrolled have a clinical response, then accrual will continue until a total of 21 evaluable patients have been enrolled in each cohort.

Note: As stated in Section **8.2**, up to 6 patients enrolled at the MTD will count towards the accrual in the Phase II portion of the trial if they are evaluable for response and if they would be fully eligible for enrollment in the Phase II portion of the trial.

3.2 PROTOCOL STOPPING RULES

New subject enrollment to the protocol will be temporarily halted if any of the following conditions are met, and consideration will be given to the need for protocol revisions regarding safety, if applicable. Consultation with the FDA may be arranged by the Sponsor before or after the protocol amendment is submitted to the NIH Intramural IRB, as needed.

- During the Phase I portion of the study If two DLTs, as described in Section **3.1.4**, occur at Dose Level 1.
- During the Phase II portion of the study Once five or more patients have been enrolled, if 20% or more patients cumulatively enrolled develop a DLT, as described in Section 3.1.4.
- During the Phase I and II portions of the study Any death that is at least possibly attributed to the investigational agent and which occurs within 30 days of receiving the investigational agent.

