required to perform the initial safety evaluation. In order to complete the dose escalation phase and Phase II, a total of up to 18+46 =64 patients may be required (allowing up to 2 inevaluable patients per Phase II cohort). Up to 6 patients enrolled at the MTD will count towards the accrual in the Phase II portion of the trial if they are evaluable for response and if they would be fully eligible for enrollment in the Phase II portion of the trial. Provided that about 2-3 patients per month will be able to be enrolled onto this trial, approximately 2-3 years may be needed to accrue the maximum number of required patients. However, as adequate responses to proceed to the second stage of accrual may not occur, the trial may end up accruing many fewer patients.

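### The Phase II DLT pause in 3.2 cannot act before the fifth patient, so two or more DLTs among the first four Phase II patients trigger no numeric pause; a one-clause fix has a small benefit and almost no cost

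*Combined protocol and SAP*

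**What the plan says.** Section 3.2 has one Phase II trigger based on a DLT count: "Once five or more patients have been enrolled, if 20% or more patients cumulatively enrolled develop a DLT". The halt is temporary and applies to new enrollment to the protocol as a whole. The only other DLT-count trigger in 3.2 concerns Dose Level 1 in Phase I. A possibly related death within 30 days of receiving the agent also halts enrollment, in either phase and with no minimum number of patients.

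The Phase I rule in 3.1.5 is stricter at small numbers: "If a level with 2 or more DLTs in 3-6 patients has been identified, patients will be accrued at the next-lowest dose level". The same section says "The protocol will enroll three patients at Dose Level 3 unless a patient experiences a DLT". It defines the MTD as the highest dose with at most 1 of 6 DLTs, or "the highest dose level studied if DLTs are not observed at any of the dose levels". An MTD of Dose Level 3 can therefore rest on three patients.

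On who counts, 3.1.7 says that "up to 6 patients enrolled at the MTD will count towards the accrual in the Phase II portion of the trial", subject to response evaluability and Phase II eligibility. It does not link this to the DLT rule. "The Phase II portion of the protocol will consist of two cohorts": melanoma (2a), and gastrointestinal or genitourinary cancer (2b). DLT assessment "will occur during the 21 days after the first vaccination for each patient" (3.1.4).

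**The concern.** Early Phase II is where experience with the chosen dose is thinnest, and it brings in new populations: under 2.1.1.1, Phase I takes only gastrointestinal cancer. If the count covers Phase II patients only, four DLTs in the first four patients would set off no numeric pause.

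This does not fit the protocol's own Phase I standard. Suppose Phase I ends with 0/3 at Dose Level 3 and two of the first three Phase II patients then have DLTs. Added to the Phase I patients, that is 2/5 or 2/6 at one dose, which meets the 3.1.5 de-escalation criterion. Section 3.2 stays silent until a fifth Phase II patient is enrolled.

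At stake are a few more enrollments at a dose whose observed DLT rate is already at or above the protocol's 20% limit.

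**Working it through.** **Inputs.** From 3.2: the rule starts at n = 5 and pauses if DLTs/n ≥ 0.20. From 3.1.5: three patients at Dose Level 3 if no DLT, or six. From 8.2: two cohorts of up to 21 evaluable patients, so 42. The documents give no operating characteristics for this rule, so there is no stated figure to reproduce, and no true DLT rate p. I assume p = 10%, 1/6, 30% and 1/3, with independent DLTs and pooled cohorts. I also assume that each DLT is known before the next enrollment, which makes the avoided enrollments an upper bound.

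**Step 1: the existing boundary, Phase II count only.** For n = 1 to 4 there is no limit. At n = 5 one DLT is enough (1/5 = 20%). For n = 6 to 10 two are needed, and at n = 11 three.

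**Step 2: how much earlier the pause would come.** If the second DLT occurs at patient 2, 3 or 4, the existing rule acts at patient 5, after 3, 2 or 1 further enrollments. The probability that the second DLT falls at patient k is (k−1)p²(1−p)^(k−2). The expected number of further enrollments is E = 3·P(2) + 2·P(3) + 1·P(4).

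| p | P(2) | P(3) | P(4) | Sum = P(≥2 of 4) | E |
|---|---|---|---|---|---|
| 10% | 0.010 | 0.018 | 0.024 | 0.052 | 0.090 |
| 1/6 | 0.028 | 0.046 | 0.058 | 0.132 | 0.234 |
| 30% | 0.090 | 0.126 | 0.132 | 0.348 | 0.654 |
| 1/3 | 0.111 | 0.148 | 0.148 | 0.407 | 0.778 |

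**Step 3: jointly with a DLT-free Phase I at that dose.** Multiply by (1−p)³ for 0/3 or (1−p)⁶ for 0/6.

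| p | (1−p)³ | P(0/3 and ≥2 of first 4) | E × (1−p)³ | (1−p)⁶ | E × (1−p)⁶ |
|---|---|---|---|---|---|
| 10% | 0.729 | 0.038 | 0.07 | 0.531 | 0.05 |
| 1/6 | 0.579 | 0.076 | 0.14 | 0.335 | 0.08 |
| 30% | 0.343 | 0.119 | 0.22 | 0.118 | 0.08 |
| 1/3 | 0.296 | 0.121 | 0.23 | 0.088 | 0.07 |

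The narrower event, 0/3 and then two or more DLTs in the first three Phase II patients, is the one inside the 3.1.5 criterion. Its probability is 0.020, 0.043, 0.074 and 0.077.

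**Step 4: cost in extra pauses.** Two DLTs in the first four patients give at least 2/5 = 40% at patient 5, so the existing rule fires there anyway. An exact recursion over patients 5 to 42 gives a chance of ever pausing of 0.497 at p = 10% and 0.780 at 1/6. Both values are unchanged when the early clause is added.

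**Step 5: if Phase I patients at the MTD are counted.** With three DLT-free patients counted, a second DLT at Phase II patient 2, 3 or 4 gives 2/5, 2/6 or 2/7. With six counted, it gives 2/8, 2/9 or 2/10. All are at or above 20%, so the existing rule fires no later than the second DLT and there is no gap. With 1 of 6 counted, a single DLT among the first four Phase II patients is enough (2/7 to 2/10).

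**The case against.** **The gap depends on the reading.** Section 3.2 does not define its denominator, and 3.1.7 lets up to six MTD patients count towards accrual. If DLT-free ones also count for DLTs, nothing is missing (Step 5). That stands as a condition. But the bullet is framed for the Phase II portion, and counting six MTD patients, or all of Phase I, would leave the five-patient threshold with nothing to do. Phase II-only is therefore the more natural reading.

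**The existing rule is already strict.** On that reading, any single DLT in the first five patients pauses enrollment by patient five. The chance is 1 − (1−p)⁵, or 41% at 10%, 60% at 1/6 and 83% at 30%. This stands; what is missing is at most a few enrollments' delay.

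**Enrollment may outrun the information.** Section 8.2 says: "Provided that about 2-3 patients per month will be able to be enrolled onto this trial". In 21 days that is 21/30.4 × 2 = 1.4 to 21/30.4 × 3 = 2.1 patients, so a DLT seen late leaves the clause little to prevent. This stands.

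**Other safeguards act from the first patient.** The related-death halt, weekly team review with enrollment decisions based on toxicity (7.6.1) and expedited reporting of serious adverse events (7.3) all apply. None sets a DLT number.

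**Stronger readings that a reader might infer.** One is that eight patients could be enrolled, four per cohort, before the rule acts. That needs a per-cohort count, which is strained: the halt covers the whole protocol, and 3.2 does not mention cohorts, whereas the response rule in 3.1.7 is expressly per cohort. Another is that the undefined denominator makes the rule's behaviour swing widely. Counting DLT-free MTD patients does lower the chance of a pause at p = 1/6 from 0.78 to 0.62 (three counted, 39 further) or 0.40 (six counted, 36 further). But 3.1.5 also permits 1 of 6, and counting that gives 0.73 at 1/6 and 0.44 at 10%, close to 0.78 and 0.50. The missing definition is a wording matter. It does not show that the rule fails.

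**Conclusion.** The point holds on the Phase II-only, pooled reading. Before the fifth Phase II patient no DLT count pauses enrollment, although Phase I would de-escalate at two or more DLTs in three to six patients and the MTD may rest on three.

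The benefit of closing the gap is small. The pause would come one to three enrollments earlier, with an expected 0.07 to 0.23 enrollments avoided jointly with 0/3 in Phase I, and 0.05 to 0.08 jointly with 0/6. These figures rest on assumed true DLT rates of 10% to 1/3, independence and immediate knowledge of each DLT. The documents do not support inferring that early Phase II patients are unprotected, because the other safeguards apply throughout. The change is worth considering because it costs so little.

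**What to change.** Add to the Phase II bullet in 3.2: *or if two or more DLTs occur among the first four Phase II patients (cohorts 2a and 2b combined)*. Leave the 20% limit from the fifth patient unchanged.

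The cost is one clause, with no extra patients or data. The downside is that a temporary pause occasionally comes one to three enrollments earlier, with no change in the overall chance of a pause on the Phase II-only count. A single early DLT still causes no pause before patient five on that count.
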